### 1.5 Justification for Dose and Regimen

[figure not shown]
Pemigatinib will be administered at 13.5 mg QD, continuously, for a cycle. Each cycle is 3 weeks. This dose and dosing schedule was selected based on emerging clinical and safety data from the INCB 54828-101 study, where the continuous dosing regimen has been tested in 12 and 14 participants at 9 mg and 13.5 mg QD continuous administration, respectively. In Study INCB 54828-101, the emerging safety data demonstrated that tolerability of the continuous dosing regimen of pemigatinib was comparable to that of intermittent dosing.

The hypothesis with a targeted therapy is that continued inhibition of the aberrant receptor may increase the potential for benefit from the treatment. Therefore, administering pemigatinib continuously will allow that consistent inhibition of the aberrant FGFR receptor in this population. Continuous dosing would still allow for dose holds for safety reasons with criteria and procedures for dose interruptions and adjustments clearly outlined in the Protocol.

Hyperphosphatemia is an expected on-target pharmacological effect of FGFR inhibition. The incidence of hyperphosphatemia, defined as any post-baseline phosphate level exceeding 5.5 mg/dL, has been observed in the majority of study participants treated with pemigatinib (refer to the IB for complete data). Some participants do not achieve hyperphosphatemia, and it is estimated that pharmacological concentration of pemigatinib in these participants is lower (see Figure 2). Therefore, up titration of pemigatinib will be used to increase the exposure of pemigatinib in participants who do not achieve hyperphosphatemia when treated with 13.5 mg QD. The goal is to increase the serum concentration of pemigatinib.

The increase in serum phosphorus observed after treatment with pemigatinib was exposure-dependent and followed a sigmoid relationship. A population Emax model of pemigatinib AUC and maximal serum phosphate change from baseline was developed. For those participants treated with pemigatinib 13.5 mg who did not develop hyperphosphatemia, AUC for pemigatinib 18 mg was estimated using a linear exposure relationship. Maximal serum phosphate change from baseline for each individual was then estimated using a population model. The maximal serum phosphate after treatment with pemigatinib 18 mg was calculated by adding the baseline of serum phosphate. The simulation suggested that the serum phosphate would increase above 5.5 mg/dL after treatment with pemigatinib 18 mg for the participants treated with pemigatinib 13.5 mg who did not develop hyperphosphatemia.

Figure 2: Comparison of Steady State Exposures for Pemigatinib 13.5 mg QD Between Subjects With Nonhyperphosphatemia and Hyperphosphatemia

AUCss = area under the curve at steady state; Css, min = minimum blood plasma concentration at steady state; HP = hyperphosphatemia.

Any participant who does not reach the target serum phosphate level of  $> 5.5$  mg/dL at any time during Cycle 1, and who is compliant with taking study drug and does not experience an ongoing Grade 2 or higher treatment-related AEs, will increase the daily dose to 18 mg starting at Cycle 2 Day 1. Participants who are titrated up to 18 mg QD will begin the next cycle at the new dose level and must agree to all Cycle 1 assessments (PK and safety assessments [hematology and blood chemistry]). Up-titration may occur no earlier than on Day 1 of Cycle 2, so that participants are observed for phosphate level and AEs at least for 1 cycle.

For participants who are up-titrated from 13.5 mg to 18 mg, a maximum of 2 dose level reductions is also recommended: 18 mg can be decreased to 13.5 mg, and if additional dose reduction is required, participants can decrease to 9 mg. Dose reductions below 9 mg are not allowed."

[figure not shown]
A CYP3A4-mediated drug-drug interaction study (INCB 54828-104) indicated there is evidence of a clinically significant effect on pemigatinib exposure when co-administered with a potent CYP3A4 inhibitor, itraconazole (increased pemigatinib AUC by 88%) or

potent CYP3A4 inducer, rifampin (decrease pemigatinib AUC by 85%). A PBPK model was developed and validated using in vitro and clinical DDI data. PBPK model-simulated pemigatinib AUCs were increased by approximately 50% for moderate CYP3A4 inhibitors and decreased by more than 50% for moderate CYP3A4 inducers. In addition, PBPK modeling shows no DDI effect when pemigatinib was coadministered with a weak CYP3A4 inhibitor or inducer.

[figure not shown]
## 1.6 Pharmacokinetic/Pharmacodynamic Summary

Pemigatinib exhibited linear pharmacokinetics (PK) over the dose range evaluated, with rapid oral absorption and a biphasic elimination, with a terminal half-life range of 10.9 to 31.4 hours. The projected average inhibition of FGFR2 based on PK and *in vitro* potency of Pemigatinib ranged from 41% at 1 mg to 97% at 20mg. Consistent with this projection, the observed inhibition of pFGFR2 in KATOIII cells spiked to *ex vivo* whole blood samples collected from subjects at trough was 82% after the 13.5 mg QD dose and 64% after the 9 mg QD dose. The steady-state plasma concentration of Pemigatinib after 13.5 mg QD dose that exceeded *in vivo* IC50 over a 24-hour dosing period is shown in Figure 1.

**Figure 11: Pemigatinib Plasma Concentrations (Mean  $\pm$  SE) at Steady State After 13.5 mg QD Oral Doses of Pemigatinib (Studies INC 54828-101 Parts 1 and 2, N = 53 and INC 54828-102, N = 17)**

The magnitude and frequency of hyperphosphatemia was also dose dependent. In the 9 mg cohorts of Part 1 and Part 2, 4 of the 6 patients experienced hyperphosphatemia. In the 13.5 mg cohort of Part 1, all 6 subjects developed hyperphosphatemia, which was managed with a low-phosphate diet and introduction of phosphate binders. Further, the increase in serum phosphorus observed after treatment with Pemigatinib was exposure-dependent (see Figure 2).

**Figure 2: Serum Phosphate Versus Exposure**

Therefore, based on a manageable safety profile and favorable PK/PD profile, the dose for this Phase 2 study is 13.5 mg.

### 1.7 Phototoxicity

There are no preclinical data available to date on the potential phototoxicity of Pemigatinib. Therefore, subjects enrolled in this study will be instructed by the site staff to take precaution to protect themselves from the sun/ultraviolet light. This includes wearing long sleeves, long trousers, hats, and sunglasses.

### 1.8 Correlative Research

#### 1.81 Peripheral blood samples

Advances in next-generation sequencing (NGS) technology have allowed for the opportunity to better understand the relationship between tumor biology and the genomic landscape. However, serial sampling of tumor tissues is challenging in most tumor types given the anatomic location and requirement of adequate quantity of tumor cells among a background of normal cells and stroma. Thus, the emergence of the “liquid biopsy” and advances in sequencing technology allow for the opportunity to serially monitor the dynamics of specific tumor mutations (Amodovar, et al, 2018; Montagut, et al, 2018; Strickler, et al, 2018). Diaz and colleagues were one of the first groups to show that *KRAS* mutations could be detected in the sera of CRC patients who, before receiving monotherapy with panitumumab, were *KRAS* wildtype (Diaz, et al, 2012). Strickler *et al.* performed large-scale genomic profiling of cell-free DNA (cfDNA) from patients with CRC and observed genomic alterations at frequencies comparable to databases with large-scale tumor sequencing data (Strickler, et al, 2018) (i.e., The Cancer Genome Atlas and Genomics Evidence Neoplasia Information Exchange). Specifically, these authors reported the ability to detect, with adequate sensitivity, *RAS* mutations and mutations in the extracellular domain of

EGFR in cfDNA. A recent clinical trial evaluating a novel EGFR mAb (Sym004) in *RAS* wildtype CRC patients that have progressed on panitumumab or cetuximab analyzed circulating tumor DNA throughout treatment and observed the emergence of extremely heterogeneous molecular landscapes where subclones with distinct resistance mechanisms coexist in one patient (Montagut, et al, 2018). Another recent clinical trial observed the emergence of *KRAS* and *NRAS* mutations upon disease progression in *BRAF*-mutant CRC patients who were receiving a triplet drug combination designed to inhibit *BRAF*, EGFR, and MEK (Corcoran, et al, 2018). Thus, analyzing cfDNA is becoming a viable clinical technique to serially monitor the emergence of resistance mechanisms that are driving the observed disease progression in CRC.

Serial blood samples will be collected throughout the study according to the test table to analyze dynamic changes in cfDNA as a function of treatment. The objective is to explore the potential mutational patterns that could be associated with tumor response and disease progression. Samples will be collected from all patients. Any detected single nucleotide variants, insertions and deletions of any length, chimeric gene fusions that arise through chromosomal rearrangement, and copy number gain or copy number loss will be recorded longitudinally for each patient.

#### 1.82 Archival tissue

Archival tissue, if available, will be collected from each patient. Molecular profiling will be performed on the available tissue. Concordance results between tissue and the subsequent liquid biopsy results will be assessed.

### 2.0 Goals

#### 2.1 Primary

2.11 To assess overall response rate (ORR) of Pemigatinib in patients with metastatic or unresectable colorectal cancer harboring activating FGFR alterations.

#### 2.2 Secondary

2.21 To assess the clinical benefit rate (complete response + partial response + stable disease ) with Pemigatinib .

2.22 To assess progression free survival (PFS) and overall survival (OS) with Pemigatinib.

2.23 Assess changes in patient quality of life (QOL) as measured by the linear analogue self-assessment (LASA) questionnaire.

2.24 Assess the frequency and severity of adverse events.

#### 2.3 Correlative Research

2.31 To assess plasma pharmacodynamic biomarkers of response and resistance to

therapy.

2.32 To explore any correlation between tissue and blood based biomarkers and clinical outcomes.

### 3.0 Patient Eligibility

**NOTE: Waivers to eligibility criteria are not allowed per ACCRU policy**

3.1 Registration – Inclusion Criteria

3.11 Histologically or cytologically confirmed diagnosis of metastatic or unresectable colorectal cancer (mCRC), based on documentation from local or outside review of pathology according to each site's established institutional procedure

3.12 Documentation of an activating genomic alteration(s) in FGF/FGFR1-3 (gain of function mutations, translocations, and amplifications allowed) in tumor tissue or blood tested at a Clinical Laboratory Improvement Amendments (CLIA) – certified laboratory.

3.13 Provide informed written consent.

3.14 Age  $\geq$  18 years.

3.15 Patient must have received and progressed on, or be intolerant to, each of the following treatments for mCRC (or have contraindication to these treatments):

- Fluoropyrimidine.
- Oxaliplatin.
- Irinotecan.
- Pembrolizumab
- Nivolumab
- Anti-VEGF (vascular endothelial growth factor) monoclonal antibody, if eligible for this therapy.
- Anti-EGFR (epidermal growth factor receptor) monoclonal antibody, if eligible for this therapy.

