## 12.0 Descriptive Factors

- 12.1 ECOG PS: 0 vs. 1. vs. 2
- 12.2 Disease characteristics: Unresectable vs. Metastatic.
- 12.3 Prior treatment: TAS-102 vs. Regorafenib vs. neither vs both (TAS-102 and Regorafenib)
- 12.4 Primary tumor location: cecum vs. ascending vs. hepatic flexure vs. transverse vs. splenic flexure vs. descending vs. sigmoid vs. rectosigmoid vs. rectum vs other.
- 12.5 Microsatellite instability or mismatch repair deficiency tested: Yes vs. no.
  - 12.5.1 If yes, MSI-High (MSI-H) vs. microsatellite stable/MSI-Low (MSS/MSI-L); loss of mismatch repair protein (MMR deficient, dMMR) vs. mismatch repair proteins intact (MMR proficient, pMMR).
- 12.6 KRAS (mutated vs. wildtype vs. unknown)
- 12.7 NRAS (mutated vs. wildtype vs. unknown)
- 12.8 BRAF V600E (mutated vs. wildtype vs. unknown)

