## 13.0 Treatment/Follow-up Decision at Evaluation of Patient

- 13.1 Patients who have CR, PR, or SD will continue treatment per protocol up to 35 cycles. After 35 cycles, patients will go to event monitoring.
- 13.2 Patients who develop PD while receiving therapy will go to the event-monitoring phase.
- 13.3 Patients who go off protocol treatment for reasons other than PD or alternative therapy will go to the event-monitoring phase per Section 18.0.
- 13.4 Event monitoring is every 3 months for 3 years after registration. If patient is still alive 3 years after registration, no further follow up is required.
- 13.5 A patient is deemed *ineligible* if after registration, it is determined that at the time of registration, the patient did not satisfy each and every eligibility criteria for study entry. The patient may continue treatment off-protocol at the discretion of the physician as long as there are no safety concerns, and the patient was properly registered. The patient will go directly to the event-monitoring phase of the study (or off study, if applicable).
  - If the patient received treatment, all data up until the point of confirmation of ineligibility must be submitted. Event monitoring will be required per Section 18.0 of the protocol.

- If the patient never received treatment, On-study material and the Off Treatment Form must be submitted. No further data submission is necessary.

13.6 A patient is deemed a *major violation*, if protocol requirements regarding treatment in cycle 1 of the initial therapy are severely violated that evaluability for primary end point is questionable. All data up until the point of confirmation of a major violation must be submitted. The patient will go directly to the event-monitoring phase of the study. The patient may continue treatment off-protocol at the discretion of the physician as long as there are no safety concerns, and the patient was properly registered. Event monitoring will be required per Section 18.0 of the protocol.

13.7 A patient is deemed a *cancel* if he/she is removed from the study for any reason before any study treatment is given. On-study material and the Off Treatment Form must be submitted. No further data submission is necessary.

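### Section 3.15 lists pembrolizumab and nivolumab without the eligibility qualifier its anti-VEGF and anti-EGFR bullets carry, leaving it unclear which patients qualify and who counts in the primary ORR

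*Combined protocol and SAP*

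**What the plan says.** Section 3.15 sets the prior-therapy requirement: "Patient must have received and progressed on, or be intolerant to, each of the following treatments for mCRC". The lead-in then adds a further route, so that the requirement covers "each of the following treatments for mCRC (or have contraindication to these treatments". A patient can therefore meet each bullet by progression, by intolerance or by contraindication. Seven bullets follow:

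- Fluoropyrimidine, oxaliplatin and irinotecan have no qualifier.
- "Pembrolizumab" stands alone as a bullet, and nivolumab follows as a separate bullet in the same bare form.
- The last two are qualified: "Anti-VEGF (vascular endothelial growth factor) monoclonal antibody, if eligible for this therapy" and "Anti-EGFR (epidermal growth factor receptor) monoclonal antibody, if eligible for this therapy".

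The note at the head of section 3.0 reads "Waivers to eligibility criteria are not allowed per ACCRU policy". Section 12.5 records, as a descriptive factor, "Microsatellite instability or mismatch repair deficiency tested: Yes vs. no". For tested patients, 12.5.1 has categories for MSI-High and for MSS/MSI-Low, and for deficient and proficient mismatch repair.

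Section 13.5 makes a patient ineligible if it is found after registration that at registration "the patient did not satisfy each and every eligibility criteria for study entry". Such a patient goes directly to event monitoring. Sections 16.11 and 16.311 limit the primary ORR to patients who are eligible, consented, treated and not major violations.

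**The concern.** The list treats contraindication and eligibility for a therapy as two different ideas. The contraindication clause in the lead-in already governs all seven bullets, yet two bullets carry an eligibility qualifier as well. If contraindication covered anyone for whom a drug is simply not indicated, that qualifier would add nothing. The natural inference is that contraindication is narrower, and the protocol does not define it.

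Two kinds of patient are then left unclear:

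- one who was never a candidate for a PD-1 antibody and has no contraindication in the strict sense;
- one who progressed on one of the two drugs and never received the other, because the lead-in demands each.

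What is at stake is statistical as well as editorial. With waivers barred, a site cannot settle a case by exception. A strict site turns such a patient away from a rare molecular subset. A permissive site enrols the patient, who may later be ruled ineligible and drop out of the ORR denominator. Section 13.5 sets no time limit on that ruling, so in a single-arm trial decided by 3 responses in 21 it could be made with the response known.

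**Working it through.** **Inputs.** ORR of 5% under the null and 20% under the alternative (16.21, 16.24). Stop if 0 responses in the first 12 evaluable patients; favourable result if 3 or more in 21 (16.211, 16.212). Three extra patients for ineligibility, cancellation, major treatment violations or other reasons, giving 24 (16.22).

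**Step 1: the plan's own figure.** Let X be the responses among the first 12, and let Y be those among the remaining n − 12. The probability of a favourable result is

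P(X=1)·P(Y≥2) + P(X=2)·P(Y≥1) + P(X≥3).

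At an ORR of 20%, P(X=1) = 0.2062, P(X=2) = 0.2835 and P(X≥3) = 0.4417. For n = 21, Y has 9 patients, with P(Y≥2) = 0.5638 and P(Y≥1) = 0.8658. Hence

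0.2062 × 0.5638 + 0.2835 × 0.8658 + 0.4417 = 0.1162 + 0.2454 + 0.4417 = 0.803.

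The same calculation at 5% gives 0.080, which matches the tabulated 0.08. The plan states 82% power. That equals the single-stage value (3 or more of 21, 82.1%) and is within 2 points of the exact two-stage value. The difference is a separate matter; the two-stage value is the baseline here.

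**Step 2: how much ineligibility the allowance absorbs.** 24 − 21 = 3, and 3/24 = 12.5%, shared by all causes of non-evaluability. A fourth loss gives 24 − 4 = 20.

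**Step 3: power below 21 evaluable.** The 0-of-12 and 3-response rules are kept, and exclusion is assumed unrelated to response.

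| Evaluable | P(Y≥2) | P(Y≥1) | Power at ORR 20% |
|---|---|---|---|
| 21 | 0.5638 | 0.8658 | 80.3% |
| 20 | 0.4967 | 0.8322 | 0.1024 + 0.2359 + 0.4417 = 78.0% |
| 19 | 0.4233 | 0.7903 | 0.0873 + 0.2240 + 0.4417 = 75.3% |

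**Step 4: exclusion that is related to response.** Suppose 3 of 21 respond, which is a favourable result. If one responder is then ruled ineligible under 3.15, 2 responses remain in 20. Unless a replacement evaluable patient responds, the result becomes unfavourable. One reading of one word can therefore reverse the conclusion.

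**Step 5: what cannot be computed.** The documents give no MSI-High prevalence, no share of candidates with prior PD-1 treatment and no definition of contraindication. The number of patients affected cannot be derived from them.

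**The case against.** The best case against the point has several parts.

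- *Contraindication and intolerance are open routes.* This stands against a reading, which 3.15 might invite, that every patient must have taken both drugs. The text does not say that. The ambiguity about non-candidates and about patients treated with only one of the two remains.
- *The three chemotherapy bullets also lack the qualifier, so its absence does not prove an intent to exclude.* This is fair. The point needs no such intent, only that the rule fails to say how these patients are classified.
- *Section 12.5 is a recording list, not an eligibility rule.* Correct: a microsatellite-stable or untested patient could enter by any of the three routes. The protocol text also does not say which patients are PD-1 candidates. The nearest pointer is a reference-list title on PD-1 blockade in mismatch-repair-deficient tumours. This is a tension between sections, not a contradiction.
- *Section 6.14 verifies eligibility before registration is accepted.* This should settle many cases at entry, but 13.5 still allows a later finding of ineligibility.
- *Lost accrual and later exclusion are alternatives for any one patient.* This stands, and the two harms should not be added together.
- *The extra 3 patients are anticipated and the 24 is a projection, while the rule counts evaluable patients.* Accrual could therefore be extended to reach 21. That would avoid the power loss at the price of time, at an expected 1 patient per month (16.23).

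**Conclusion.** The point holds as an internal inconsistency with consequences for the primary analysis. Section 3.15 does not clearly admit a patient who was never a PD-1 candidate or who progressed on only one of the two drugs. Sections 13.5 and 16.11 then make that unresolved question decide membership of the ORR denominator.

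The demonstrable size is modest: 2.3 points of power for one evaluable patient below 21 (80.3% to 78.0%) and 5.0 points for two (to 75.3%). This assumes that the full allowance of 3 is already used, that accrual is not extended and that exclusions are unrelated to response. The larger risk is a classification made with the response known, which could turn a 3-response result into a 2-response one.

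A reader might go further and infer that most candidates are excluded, or that patients already treated are ineligible. The documents support neither. The first needs a prevalence or treatment rate they do not give, and the second needs the narrowest reading of contraindication together with enrolment data they do not contain. For the same reason no multiplier should be applied to the roughly 500 screened or to the accrual rate.

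**What to change.** Reconcile 3.15 with its own list and with 12.5:

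- Add to the pembrolizumab and nivolumab bullets the eligibility qualifier that the anti-VEGF and anti-EGFR bullets already carry.
- Have the sponsor state whether progression on one of the two drugs is sufficient or both are needed. That is the sponsor's decision, and nothing in the documents settles it.
- Bring the eligibility checklist into line.
- If any affected patient has been registered, fix the classification by a written rule applied without reference to response.

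The decision rules, the 21 evaluable patients and the projected accrual of 24 stay as they are. The cost is a small protocol amendment with IRB handling and a revised checklist.

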3.16 Measurable disease as defined in Section 11.0

3.17 ECOG Performance Status (PS) of 0, 1, or 2. Form is available on the ACCRU web site.

3.18 The following laboratory values obtained  $\leq$  28 days prior to registration:

- Absolute neutrophil count (ANC)  $\geq$  1500/mm^3.

- Platelet count  $\geq 100,000/\text{mm}^3$ .
- Hemoglobin  $\geq 9.0 \text{ g/dL}$ .
- Total bilirubin  $\leq 1.5 \times$  upper limit of normal (ULN), or  $\leq 2.5 \times$  ULN if patient has Gilbert syndrome or disease involving the liver.
- Aspartate aminotransferase (AST) and alanine aminotransferase (ALT)  $\leq 2.5 \times$  ULN (or  $\leq 5 \times$  ULN in presence of suspected liver metastases).
- Serum phosphate  $<$  institutional ULN.
- Serum calcium within institutional normal range, or serum albumin-corrected calcium within institutional normal range (if serum albumin is outside of the institutional normal range).
- Potassium levels  $>$  institutional lower limit of normal (supplementation can be used to correct potassium level during screening).
- Serum creatinine  $\leq 1.5 \times$  ULN, or calculated creatinine clearance  $> 30 \text{ mL/min}$  using the Cockcroft-Gault formula (see below) or 24-hours urine collection analysis:

Cockcroft-Gault Equation:

$$\text{Creatinine clearance for males} = \frac{(140 - \text{age})(\text{weight in kg})}{(72)(\text{serum creatinine in mg/dL})}$$

$$\text{Creatinine clearance for females} = \frac{(140 - \text{age})(\text{weight in kg})(0.85)}{(72)(\text{serum creatinine in mg/dL})}$$

3.19 Corrected QT interval (QTc) by Fridericia's method (QTcF) assessed by electrocardiogram (ECG) completed  $\leq 28$  days prior to registration, and resulted as:

- QTcF  $\leq 450 \text{ msec}$  in men, or
- QTcF  $\leq 470 \text{ msec}$  in women.

3.19a Negative serum pregnancy test completed  $\leq 7$  days prior to registration, for women of childbearing potential only. See Appendix I for definition of WOCBP.

3.19b Willing to provide tissue and blood samples for correlative research purposes (see Sections 6.0, 14.0 and 17.0).

3.19c Willing to allow transfer of tissue and blood samples, clinical information, and outcome data collected from this trial for future research (see Sections 6, 14, and 17).

